# 4.6.1.ITT ALL PATIENTS: INTRACRANIAL PROGRESSION-FREE SURVIVAL (IPFS).

0 patient has been censored at time 0 due to lack of tumor assessments.

Table 72: iPFS (event). ITT All patients

PFS (event)	N	%	95%CI
Censored			
Event (PD/death)			
Total			

Table 73: Median iPFS. ITT All patients

	Median	95%CI
PFS		

### iPFS estimated at 3, 6 and 12 months (Kaplan-Meier)

Table 74: iPFS at 3, 6 and 12 months. ITT All patients

iPFS	Events (%, total N)	Patients at risk	% estimated cumulative survival ratio	95% IC
At 3 months				
At 6 months				
At 12 months				

<sup>1Estimated using Kaplan-Meier product-limit method

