#### 2. Secondary objectives:

[figure not shown]
- a. Intracranial objective response rate assessed by the investigators using modified RECIST 1.1 before local treatment in cohort 2.
- b. Intracranial objective response rate assessed by the investigators using modified RECIST 1.1 before local treatment in cohort 1.
- c. The duration of the intracranial response in both cohorts assessed by the investigators using modified RECIST 1.1.
- d. The intracranial progression free survival by modified RECIST in both cohorts
- e. Percentage of patients free of intracranial progression according to modified RECIST at 6 (week 24), 12 (week 48) and 24 months (week 96) in both cohorts.
- f. Percentage of patients free of extracraneal progression according to RECIST 1.1 () at 6 (week 24), 12 (week 48) and 24 months (week 96) in both cohorts.
- g. Overall survival in both cohorts.
- h. Percentage of alive patients at 6, 12 and 24 months in both cohorts.
- i. Toxicity of the combination until local treatment in both cohorts:
  - Toxicity of the combination after local treatment in both cohorts.
  - Quality of life in both cohorts.

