# 10.2. Study endpoints

Intracranial objective response (iORR) rate by modified RECIST 1.1 before local treatment in cohort 1 and 2: iORR calculated as the proportion of patient with a best overall intracranial response of complete response (CR) or partial response (PR) before local treatment in cohort 1 and 2. The final statistical analysis of this endpoint is expected to be performed within 3 months after the local treatment of the last patient in any cohort. iORR will be also reported separately for both cohorts.

**Duration of intracranial response in both cohorts (iDOR):** Calculated as the time from the date of first documented CR or PR to the first documented intracranial progression or death due to underlying cancer, in patients with documented intracranial CR or PR before local treatment. The final statistical analysis of this endpoint is expected to be performed within 6 months after database closure expected at 24 months after last patient inclusion, however interim analysis might be performed when analysing other primary variables.

The intracranial progression free survival (iPFS) by modified RECIST in both cohorts: iPFS is defined as the time from the date of inclusion to the date of the first documented intracranial disease progression or death due to any cause, whichever occurs first. PFS will be determined based on tumour assessment (modified RECIST version 1.1 criteria). The local Investigator's assessments will be used for analyses. Those patients who are alive and have not progressed at the last follow-up, date of progression will be censored at the date of the last follow-up. Patient with no additional image test other than baseline will be censored to the day after to inclusion. The final statistical analysis of this endpoint is expected to be performed within 6 months after database closure expected at 24 months after last patient inclusion, however interim analysis might be performed when analysing other primary variables.

Percentage of patients free of intracranial progression at 6 (week 24), 12 (week 48) and 24 months (week 96) in both cohorts: percentage of patients free of intracranial progression assessed by modified RECIST at 6 months (week 24), 12 months (week 48) and 24-month (week 96) considering date of inclusion. The final statistical analysis of this endpoint is expected to be

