performed within 6 months after database closure expected at 24 months after last patient inclusion, however interim analysis might be performed when analysing other primary variables

Percentage of patients (%) free of extracraneal progression at 6 (week 24), 12 (week 28) and 24 months (week 96): percentage of patients free of progression by RECIST 1.1 at 6 months (week 24), 12 months (week 48) and 24-month (week 96) considering date of inclusion. The final statistical analysis of this endpoint is expected to be performed within 6 months after database closure expected at 24 months after last patient inclusion, however interim analysis might be performed when analysing other primary variables.

**Overall Survival in both cohorts (OS):** OS is calculated as the time from date of inclusion to date of death due to any cause. The final statistical analysis of this endpoint is expected to be performed within 6 months after database closure expected at 24 months after last patient inclusion, however interim analysis might be performed when analysing other primary variables.

Percentage of patients (%) alive at 6, 12 and 24 months in both cohorts: percentage of patients alive at 6 months, 12 month and 24-month considering date of inclusion. The final statistical analysis of this endpoint is expected to be performed within 6 months after database closure expected at 24 months after last patient inclusion, however interim analysis might be performed when analysing other primary variables.

**Toxicity of the combination until local treatment:** Number of patients with adverse events and serious adverse events, changes in laboratory values, vital signs, electrocardiograms (ECGs), LVEF (MUGA (Multigated Acquisition Scan) / echocardiogram) and assessment of physician, dermatological and ocular examinations graded according to the National Cancer Institute (NCI) Common Terminology Criteria for Adverse Events (CTCAE) v 4.03 until local treatment (local treatment D1). It will be studied using descriptive statistics techniques, such as frequency tables and contingency tables. The final statistical analysis of this endpoint is expected to be performed within 6 months after database closure expected at 24 months after last patient inclusion, however interim analysis might be performed when analysing other primary variables.

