# 4.7.3.ITT - COHORT 2: EXTRACRANIAL PROGRESSION-FREE SURVIVAL (EPFS).

Table 96: Events type PFS

PFS (event)	N	%	95%CI
Censored			
Event (PD/death)			
Total			

Table 97: Median/mean PFS (estimated by Kaplan-Meier)

	Median (months)	CI 95%	Mean	CI 95%
Progression free survival				

Table 98: PFS estimated survival ratio

PFS	Events (%, total N)	Patients at risk	% estimated cumulative survival ratio	CI 95%
At 3 months				
At 6 months				
At 9 months				
At 12				
months				
At 15				
months				

Figure 13: Progression free survival

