# 4.7.6.PP - COHORT 2: EXTRACRANIAL PROGRESSION-FREE SURVIVAL (EPFS).

Table 105: Events type PFS

PFS (event)	N	%	95%CI
Censored			
Event (PD/death)			
Total			

Table 106: Median/mean PFS (estimated by Kaplan-Meier)

	Median (months)	CI 95%	Mean	CI 95%
Progression free survival				

Table 107: PFS estimated survival ratio

PFS	Events (%, total N)	Patients at risk	% estimated cumulative survival ratio	CI 95%
At 3 months				
At 6 months				
At 9 months				
At 12				
months				
At 15				
months				

Figure 16: Progression free survival

# 4.8. QUALITY OF LIFE QUESTIONARY: EORTC QLQ C-30. COHORT 2

All scores are scaled to range from 0-100, even scores based on single items. Be aware that these single-item scales still have only 4 possible values, even though they are transformed to range from 0-100. The scale name and number of items are listed below.

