## 7.2.3. INTRACRANIAL PROGRESSION-FREE SURVIVAL (IPFS) VS SYMPTOMATIC.

Table 162: Events type PFS

Symptomatic group	
Event (PD/death)	
Censored	

1. Pearson's Chi-squared test

Table 163: Median/mean PFS (estimated by Kaplan-Meier)

	Median (months)	CI 95%	Mean	CI 95%
No				
Yes				

Table 164: PFS estimated survival ratio

PFS	Events (%, total N)	Patients at risk	% estimated cumulative survival ratio	CI 95%
No				
At 6 months				
At 12				
months				
At 18				
months				
At 24				
months				
Yes				
At 6 months				
At 12				
months				
At 18				
months				
At 24				
months				

Figure 23: Progression-free survival vs Symptomatic group

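### The SAP leaves the protocol's 24-month row out of all six iPFS landmark tables and both cohort 2 ePFS tables, and gives no reason

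*Combined protocol and SAP*

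**What the plan says.** **Protocol.** Section 4.2 lists as a secondary objective "Percentage of patients free of intracranial progression according to modified RECIST at 6 (week 24), 12 (week 48) and 24 months (week 96)", for each cohort, and lists the extracranial counterpart at the same times. Section 10.2 turns these into endpoints. The intracranial one is "Percentage of patients free of intracranial progression at 6 (week 24), 12 (week 48) and 24 months (week 96) in both cohorts". The extracranial one is the "percentage of patients free of progression by RECIST 1.1 at 6 months (week 24), 12 months (week 48) and 24-month (week 96)". Section 8.3 expects 24 months of follow-up, and section 10.2 places database closure 24 months after the last inclusion.

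**SAP, protocol populations.** The six iPFS landmark tables in section 4.6 (74, 77, 80, 83, 86, 89) sit under the subheading "iPFS estimated at 3, 6 and 12 months (Kaplan-Meier)" and have only those three rows; the first is titled "Table 74: iPFS at 3, 6 and 12 months. ITT All patients". For cohort 2 ePFS, "Table 98: PFS estimated survival ratio" (section 4.7.3, ITT) and "Table 107: PFS estimated survival ratio" (section 4.7.6, PP) have rows at 3, 6, 9, 12 and 15 months. The other four ePFS tables, and all six OS tables in section 4.5, run to 24 months.

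**SAP, other groupings.** Section 7 regroups patients at the coordinator's request into A+C (symptomatic) and B (asymptomatic). Table 161 gives 24-month iPFS for B, and "Table 164: PFS estimated survival ratio" (section 7.2.3) gives it for both groups. The addendum after the main SAP gives it by radiotherapy yes/no in ITT (its section 2.3, Table 11).

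**The concern.** Month 24 is part of the endpoint's definition, and the follow-up period was planned to reach it. If the SAP is followed as written, the 24-month percentage free of intracranial progression is not tabulated for cohort 1, cohort 2 or all patients. The extracranial percentage is not tabulated for cohort 2. The same quantity for iPFS does appear for groups the protocol never defined.

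Those groups cannot stand in for the cohorts. Group A is cohort 2, and group C consists of patients who were asymptomatic at study treatment but had earlier received corticosteroids for a symptom of the disease. Unless C is empty, A+C is not cohort 2 and B is not cohort 1.

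The late time point also bears on the trial's rationale. Protocol section 3 notes the short progression-free survival in the earlier combination trial and asks whether local therapy after an incomplete response could lengthen the duration of response.

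**Working it through.** The plan has no figure to reproduce here. The check compares the protocol's landmarks {6, 12, 24} with the rows of each SAP table.

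| SAP table(s) | Population | Rows (months) | Protocol landmark missing | Added |
|---|---|---|---|---|
| 74, 77, 80 (iPFS) | ITT: all, cohort 1, cohort 2 | 3, 6, 12 | 24 | 3 |
| 83, 86, 89 (iPFS) | PP: all, cohort 1, cohort 2 | 3, 6, 12 | 24 | 3 |
| 92, 95 (ePFS) | ITT: all, cohort 1 | 6, 12, 18, 24 | none | 18 |
| 98 (ePFS) | ITT: cohort 2 | 3, 6, 9, 12, 15 | 24 | 3, 9, 15 |
| 101, 104 (ePFS) | PP: all, cohort 1 | 6, 12, 18, 24 | none | 18 |
| 107 (ePFS) | PP: cohort 2 | 3, 6, 9, 12, 15 | 24 | 3, 9, 15 |
| 56, 59, 62, 65, 68, 71 (OS) | ITT and PP: all, cohort 1, cohort 2 | 6, 12, 18, 24 | none | 18 |
| 158 (iPFS) | A+C | 3, 6, 9, 12, 15, 18, 21 | 24 | 3, 9, 15, 18, 21 |
| 161, 164 (iPFS) | B; A+C versus B | 6, 12, 18, 24 | none | 18 |
| Addendum 11 (iPFS) | ITT by radiotherapy | 6, 12, 18, 24 | none | 18 |

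**Count.** Of the 12 iPFS and ePFS tables for protocol populations, 6 + 2 = 8 lack month 24. Each should carry three protocol landmarks, which makes 12 × 3 = 36 rows. Of these, 36 − 8 = 28 are present and 8 are missing, all at month 24.

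**Population.** SAP section 3.1 assigns secondary efficacy endpoints to PP, while the tables cover both ITT and PP. The iPFS and cohort 2 ePFS rows are missing in both, so the choice of population does not close the gap.

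**Where the landmark lies.** The protocol equates 24 months with week 96, which is 96 × 7 = 672 days. At 30.4375 days per month, 672 / 30.4375 = 22.1 calendar months. Twenty-four calendar months is 24 × 30.4375 / 7 = 104.4 weeks, about 8 weeks later. A row labelled only 24 months could therefore be computed at a different time from the protocol's endpoint.

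**Imaging near the landmark.** Scans every 8 weeks (±1 week) are scheduled only up to 12 months; after that, protocol sections 8.1 and 10.3 leave them to local practice. No week-96 scan is fixed. SAP section 4.6 censors event-free patients at their last available tumour assessment, so a patient without progression whose last scan was before week 96 is not at risk at the landmark.

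**The case against.** **The protocol allows selected time points.** Section 10.6 promises Kaplan-Meier estimates at selected times. This is general wording and does not override an endpoint whose definition names month 24.

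**The curves will show it.** iPFS figures are planned for each population, and a 24-month value might be read from them. Only their titles are available, so whether they carry numbers at risk or confidence bands is unknown. The tabulated estimate is still missing.

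**Few patients may be at risk, and late scans are unscheduled.** This stands as a limit on precision and timing, most of all in cohort 2 (N=15). It supports printing the number at risk, or *not estimable*. The SAP does not give it as a reason for dropping the row.

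**The consequence is modest.** This also stands. The endpoints are secondary and descriptive, and cohort 2 is exploratory. The primary response rate, the medians and the 6- and 12-month percentages are unaffected.

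**Stronger readings.** A reader might infer that the SAP replaced the protocol's time points. It did not: two of the three are kept in every table. A reader might also infer selective reporting, because SAP sections 3.5 and 4.6.1 contain statements that presuppose data in hand (patients still on treatment at database closure; none censored at time 0). Those statements suggest that the tables came from a completed report, but they do not show why the rows differ. The pattern has no clear direction: month 24 is tabulated for OS, for four of six ePFS tables, and for iPFS by symptom group and by radiotherapy. Group A+C stops at 21 months in Table 158 yet reaches 24 in Table 164. The documents support an unexplained inconsistency and say nothing about motive.

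**Conclusion.** The point holds in this form: one pre-specified landmark of three, month 24, has no row in 8 of 12 protocol-population tables (all 6 for iPFS; the 2 cohort 2 tables for ePFS), and no reason is stated. ePFS for cohort 1 and for all patients is complete, as is OS.

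The conclusion rests only on comparing the documents. It assumes no event rate, censoring pattern or sample size. No interval width is offered, because the documents give no expected 24-month rate or late censoring pattern from which to derive one. The correction should be made, but it does not affect the primary analysis.

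**What to change.** 1. Add a 24-month row, evaluated at week 96, with number at risk and 95% CI, to Tables 74, 77, 80, 83, 86, 89, 98 and 107. Print *not estimable* where nobody is at risk.
2. Keep 3, 9 and 15 months only as extra rows, and change the section 4.6 subheadings and table titles to match.
3. State in a footnote that the landmarks are weeks 24, 48 and 96, so that every progression table uses one convention. The extracranial heading in protocol section 10.2 prints week 28 for 12 months, while its own text and section 4.2 say week 48; cite week 48.
4. Add a note that imaging after 12 months follows institutional practice, so the 24-month progression estimate is less precise and its timing less controlled than the earlier ones.

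If the sponsor prefers to leave month 24 out, the SAP should record that as a departure from the protocol and give the reason. The cost is an edit to eight table templates and one more time point in Kaplan-Meier output that is already planned. No new data are needed.

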### Figure: intracranial Progression Free Survival (ITT: All patients)

4.6.2.ITT - COHORT 1: INTRACRANIAL PROGRESSION-FREE SURVIVAL (IPFS).

Table 75: iPFS (event). ITT Cohort 1

PFS (event)	N	%	95%CI
Censored			
Event (PD/death)			

PFS (event)	N	%	95%CI
Total			

Table 76: Median iPFS. ITT Cohort 1

	Median	95%CI
PFS		

# iPFS estimated at 3, 6 and 12 months (Kaplan-Meier)

Table 77: iPFS at 3, 6 and 12 months. ITT Cohort 1

iPFS	Events (%, total N)	Patients at risk	% estimated cumulative survival ratio	95% IC
At 3 months				
At 6 months				
At 12 months				

<sup>1Estimated using Kaplan-Meier product-limit method

### Figure: intracranial Progression Free Survival (ITT Cohort 1)

4.6.3.ITT - COHORT 2: INTRACRANIAL PROGRESSION-FREE SURVIVAL (IPFS).

Table 78: iPFS (event). ITT Cohort 2

PFS (event)	N	%	95%CI
Censored			
Event (PD/death)			
Total			

Table 79: Median iPFS. ITT Cohort 2

	Median	95%CI
PFS		

# iPFS estimated at 3, 6 and 12 months (Kaplan-Meier)

Table 80: iPFS at 3, 6 and 12 months. ITT Cohort 2

iPFS	Events (%, total N)	Patients at risk	% estimated cumulative survival ratio	95% IC
At 3 months				
At 6 months				
At 12 months				

<sup>1Estimated using Kaplan-Meier product-limit method

Figure: intracranial Progression Free Survival (ITT Cohort 2)

# 4.6.4.PP ALL PATIENTS: INTRACRANIAL PROGRESSION-FREE SURVIVAL (IPFS).

Table 81: iPFS (event). PP All patients

PFS (event)	N	%	95%CI
Censored			
Event (PD/death)			
Total			

Table 82: Median iPFS. PP All patients

	Median	95%CI
PFS		

iPFS estimated at 3, 6 and 12 months (Kaplan-Meier)

Table 83: iPFS at 3, 6 and 12 months. PP All patients

iPFS	Events (%, total N)	Patients at risk	% estimated cumulative survival ratio	95% IC
At 3 months				
At 6 months				
At 12 months				

<sup>1Estimated using Kaplan-Meier product-limit method

Figure: intracranial Progression Free Survival (PP: All patients)

4.6.5.PP - COHORT 1: INTRACRANIAL PROGRESSION-FREE SURVIVAL (IPFS).

Table 84: iPFS (event). PP Cohort 1

PFS (event)	N	%	95%CI
Censored			
Event (PD/death)			
Total			

Table 85: Median iPFS. PP Cohort 1

	Median	95%CI
PFS		

# iPFS estimated at 3, 6 and 12 months (Kaplan-Meier)

Table 86: iPFS at 3, 6 and 12 months. PP Cohort 1

iPFS	Events (%, total N)	Patients at risk	% estimated cumulative survival ratio	95% IC
At 3 months				
At 6 months				

iPFS	Events (%, total N)	Patients at risk	% estimated cumulative survival ratio	95% IC
At 12 months				

<sup>1Estimated using Kaplan-Meier product-limit method

# Figure: intracranial Progression Free Survival (PP Cohort 1)

4.6.6.PP - COHORT 2: INTRACRANIAL PROGRESSION-FREE SURVIVAL (IPFS).

Table 87: iPFS (event). PP Cohort 2

PFS (event)	N	%	95%CI
Censored			
Event (PD/death)			
Total			

Table 88: Median iPFS. PP Cohort 2

	Median	95%CI
PFS		

# iPFS estimated at 3, 6 and 12 months (Kaplan-Meier)

Table 89: iPFS at 3, 6 and 12 months. PP Cohort 2

iPFS	Events (%, total N)	Patients at risk	% estimated cumulative survival ratio	95% IC
At 3 months				
At 6 months				
At 12 months				

<sup>1Estimated using Kaplan-Meier product-limit method

### Figure: intracranial Progression Free Survival (PP Cohort 2)

# 4.7. Extracranial Progression-free survival (ePFS).

Extracranial Progression-free survival (PFS), defined as the time from inclusion (first dose of treatment) until extracranial tumour progression (RECIST 1.1) or death. Patients without any of the previous events are censored at the date of the last available tumor assessment.

# 4.7.1.ITT ALL PATIENTS: EXTRACRANIAL PROGRESSION-FREE SURVIVAL (EPFS).

Table 90: Events type PFS

PFS (event)	N	%	95%CI
Censored			
Event (PD/death)			
Total			

Table 91: Median/mean PFS (estimated by Kaplan-Meier)

	Median (months)	CI 95%	Mean	CI 95%
Progression free survival				

Table 92: PFS estimated survival ratio

PFS	Events (%, total N)	Patients at risk	% estimated cumulative survival ratio	CI 95%
At 6 months At 12 months At 18 months At 24 months				

Figure 11: Progression free survival

4.7.2.ITT - COHORT 1: EXTRACRANIAL PROGRESSION-FREE SURVIVAL (EPFS).

Table 93: Events type PFS

PFS (event)	N	%	95%CI
Censored			
Event (PD/death)			
Total			

Table 94: Median/mean PFS (estimated by Kaplan-Meier)

	Median (months)	CI 95%	Mean	CI 95%
Progression free survival				

Table 95: PFS estimated survival ratio

PFS	Events (%, total N)	Patients at risk	% estimated cumulative survival ratio	CI 95%
At 6 months At 12 months At 18 months At 24 months				

Figure 12: Progression free survival

# 4.7.3.ITT - COHORT 2: EXTRACRANIAL PROGRESSION-FREE SURVIVAL (EPFS).

Table 96: Events type PFS

PFS (event)	N	%	95%CI
Censored			
Event (PD/death)			
Total			

Table 97: Median/mean PFS (estimated by Kaplan-Meier)

	Median (months)	CI 95%	Mean	CI 95%
Progression free survival				

Table 98: PFS estimated survival ratio

PFS	Events (%, total N)	Patients at risk	% estimated cumulative survival ratio	CI 95%
At 3 months				
At 6 months				
At 9 months				
At 12				
months				
At 15				
months				

Figure 13: Progression free survival

# 4.7.4.PP ALL PATIENTS: EXTRACRANIAL PROGRESSION-FREE SURVIVAL (EPFS).

Table 99: Events type PFS

PFS (event)	N	%	95%CI
Censored			
Event (PD/death)			
Total			

Table 100: Median/mean PFS (estimated by Kaplan-Meier)

	Median (months)	CI 95%	Mean	CI 95%
Progression free survival				

Table 101: PFS estimated survival ratio

PFS	Events (%, total N)	Patients at risk	% estimated cumulative survival ratio	CI 95%
At 6 months At 12 months At 18 months At 24 months				

Figure 14: Progression free survival

# 4.7.5.PP - COHORT 1: EXTRACRANIAL PROGRESSION-FREE SURVIVAL (EPFS).

Table 102: Events type PFS

PFS (event)	N	%	95%CI
Censored			
Event (PD/death)			
Total			

Table 103: Median/mean PFS (estimated by Kaplan-Meier)

	Median (months)	CI 95%	Mean	CI 95%
Progression free survival				

Table 104: PFS estimated survival ratio

PFS	Events (%, total N)	Patients at risk	% estimated cumulative survival ratio	CI 95%
At 6 months At 12 months At 18 months At 24 months				

Figure 15: Progression free survival

# 4.7.6.PP - COHORT 2: EXTRACRANIAL PROGRESSION-FREE SURVIVAL (EPFS).

Table 105: Events type PFS

PFS (event)	N	%	95%CI
Censored			
Event (PD/death)			
Total			

Table 106: Median/mean PFS (estimated by Kaplan-Meier)

	Median (months)	CI 95%	Mean	CI 95%
Progression free survival				

Table 107: PFS estimated survival ratio

PFS	Events (%, total N)	Patients at risk	% estimated cumulative survival ratio	CI 95%
At 3 months				
At 6 months				
At 9 months				
At 12				
months				
At 15				
months				

Figure 16: Progression free survival

# 4.8. QUALITY OF LIFE QUESTIONARY: EORTC QLQ C-30. COHORT 2

All scores are scaled to range from 0-100, even scores based on single items. Be aware that these single-item scales still have only 4 possible values, even though they are transformed to range from 0-100. The scale name and number of items are listed below.

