# **Protocol specifications for trial determinations**

**Informed Consent Form (ICF):** Determinations performed by routine clinical practice before signing the informed consent will be valid, provided they are carried out following from this protocol, if they have been performed during the period included in the table 11.

**Screening registration:** Any patient that sign ICF should be registered in the EDC system and have assigned a unique screening number.

**Anamnesis:** to be performed during the baseline period in the 2 weeks prior to inclusion. Medical history will include all active conditions and any condition diagnosed considered to be clinically significant by the investigator. Melanoma history will be recorded separately and not listed as Medical History.

**Demographics:** Date of birth, race, and sex.

**Physical examination/vital signs:** Complete physical examination, weight, height, and vital signs (pulse, respiratory rate, **blood pressure** and body temperature).

**ECOG-PS:** Functional status will be assessed using the ECOG score.

**Neurological examination:** Basic neurological assessment according to normal practice and Modified Barthel Index according to "Guidelines for the Modified Barthel Index of Activities of Daily Living"

**Ophthalmologic anamnesis and evaluation by Oncologist:** ophthalmologic anamnesis and evaluation performed by oncologist as a part of physical examination and it will be performed at baseline and in every monthly visit. Only if there's any alarm symptom or sign or previous ocular antecedents, patient will be evaluated by Ophthalmologist.

**Ophthalmologist examination:** Patient will be evaluated by Ophthalmologist if there's any alarm symptom or sign or previous ocular antecedents.

**ECG:** Standard 12-lead ECG at baseline, after 4 weeks of treatment, after every 12 weeks and in the end of treatment visit. Additional ECGs may be performed at the discretion of the investigator.

**Concomitant medication:** All drugs taken within 30 days before starting the trial and concomitantly during the study will be recorded in medical records and in eCRF with indication, dose information and administration dates.

**Inclusion and Exclusion Criteria:** Verification that patients meet all inclusion criteria and none of exclusion.

Quality of Life: EORTC QLQ 30 administered at baseline, at week 8 and week 24.

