**Toxicity of the combination after local treatment:** Number of patients with adverse events and serious adverse events, changes in laboratory values, vital signs, electrocardiograms (ECGs), LVEF (MUGA (Multigated Acquisition Scan) / echocardiogram) and assessment of physician, dermatological and ocular examinations graded according to the National Cancer Institute (NCI) Common Terminology Criteria for Adverse Events (CTCAE) v 4.03 after local treatment (after end of local treatment date). It will be studied using descriptive statistics techniques, such as frequency tables and contingency tables. The final statistical analysis of this endpoint is expected to be performed within 6 months after database closure expected at 24 months after last patient inclusion, however interim analysis might be performed when analysing other primary variables.

**Quality of life:** Change from baseline in the global health status score of the EORTC QLQ-C30. The final statistical analysis of this endpoint is expected to be performed within 6 months after database closure expected at 24 months after last patient inclusion, however interim analysis might be performed when analysing other primary variables.

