# 4.8.1.GLOBAL HEALTH STATUS/QoL 4.8.1.1. QL - GLOBAL HEALTH STATUS/QoL (REVISED) (FROM 2 ITEMS)

Table 108: Global health status/QoL

Global health status/QoL	N	Mean(SD)	Median(Min-Max)	p-value (wilcoxon test) compared with baseline
Baseline				
w8				
w16				

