## 7. OTHER ANALYSES REQUIRED BY THE COORDINATOR

Group A: Symptomatic patients (Those belonging tp symptomatic cohort 2).

Group B: Asymptomatic patients, both those who were not treated with corticosteroids or anticonvulsants and those who were treated without association with brain metastases.

Group C: Patients who were asymptomatic at the time of study treatment but had been treated with corticosteroids in the days before due to a symptom of the disease.

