### 2.1.1.GLOBAL HEALTH STATUS/QoL 2.1.1.1. QL - GLOBAL HEALTH STATUS/QoL (REVISED) (FROM 2 ITEMS)

Table 1: Global health status/QoL

Global health status/QoL	N	Mean(SD)	Median(Min-Max)	p-value (wilcoxon test) compared with baseline
Baseline				
w8				
w16				

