#### 4. COHORT B (ASYMPTOMATIC PATIENTS)

Analyses were conducted exclusively on significant variables across the entire sample.

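### No SAP quality-of-life table estimates the protocol's endpoint, change from baseline in global health status, and none shows cohort 1 as its own group

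*Combined protocol and SAP*

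**What the plan says.** **Protocol.** The secondary objectives (Synopsis and section 4.2) include "Quality of life in both cohorts". Section 10.2 defines the endpoint as "Change from baseline in the global health status score of the EORTC QLQ-C30". Section 8.1 gives the schedule: "EORTC QLQ 30 administered at baseline, at week 8 and week 24". Section 10.7 says that analysis uses observed data and that values missing through drop-out are not filled in.

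**Main SAP.** Section 4.8 is headed "QUALITY OF LIFE QUESTIONARY: EORTC QLQ C-30. COHORT 2". Tables 108 to 123 have one row each for baseline, w8 and w16. Their columns are N, mean (SD), median (range) and "p-value (wilcoxon test) compared with baseline".

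**Later quality-of-life report in the same file.** The layout is the same. Section 2 covers all cohorts pooled, starting with "Table 1: Global health status/QoL". Section 3 covers groups A and C as symptomatic, and section 4 covers group B as asymptomatic. Sections 3 and 4 are limited to scales that were significant in the whole sample.

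**Groups.** SAP section 7 equates group A with cohort 2 and describes group C as "Patients who were asymptomatic at the time of study treatment but had been treated with corticosteroids" shortly before because of a disease symptom. Protocol 5.3 defines cohort 1 by the absence of active symptoms at inclusion.

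**The concern.** The endpoint is a within-patient quantity, but the tables are cross-sectional. If they are filled in exactly as laid out, the reader gets three visit means and a p-value. The reader does not get the size of the change, its uncertainty or the number of patients on whom it rests.

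The tempting substitute is to subtract the baseline row from a later row. With observed data only, those rows may describe different patients, so the subtraction can mix real change with selective drop-out.

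The objective names both cohorts, yet the larger one has no table of its own. A pre-specified secondary endpoint would then be tested but not estimated, and it could not be read for cohort 1.

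**Working it through.** **1. Is there a stated figure to reproduce?** Not for quality of life. The only sized quantity is intracranial response in cohort 1. With rates of 40% and 60%, one-sided 5% and 80% power, the normal approximation gives n = 37.1, so 38; then 38/0.8 = 47.5, so 48. Both match the protocol, but neither bears on this endpoint.

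**2. Count of the table shells.**

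| Source | Patients | Tables | With change or its CI | With paired n |
|---|---|---|---|---|
| SAP 4.8 and 4.9, Tables 108–123 | cohort 2 | 16 | 0 | 0 |
| QoL report 2, Tables 1–16 | all | 16 | 0 | 0 |
| QoL report 3, Tables 17–20 | A + C | 4 | 0 | 0 |
| QoL report 4, Tables 21–24 | B | 4 | 0 | 0 |
| Total | | 40 | 0 | 0 |

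**3. Where cohort 1 appears.** Group A is cohort 2, so group C, listed separately and asymptomatic at study treatment, comes from cohort 1. Cohort 1 is therefore B + C. It appears inside the pooled tables, and split, with B alone and C beside cohort 2. No table shows B + C. By planned size, section 4.8 covers 15/63 = 24% of patients and leaves out 48/63 = 76%.

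**4. Visits.** The protocol has week 8 and week 24; all 40 shells have w8 and w16. The later scheduled visit has no row.

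**5. What unequal rows can do (illustration).** The documents give no quality-of-life scores, SD or form completion, so every input here is assumed. Let a be the share with no later form, and g the amount by which their baseline mean lies below that of the patients who stay. Suppose that nobody changes and that the baseline row includes everyone.

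- Baseline row = stayers' mean − a × g; later row = stayers' mean.
- Apparent change = a × g.
- a = 0.20: g = 5 gives +1, g = 15 gives +3, g = 20 gives +4.
- g = 0 gives 0; a negative g reverses the sign.

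**6. Does paired change remove this?** A simulation (SD 20; 15 or 63 patients; 4,000 runs; leaving correlated 0.5 with baseline score) gave:

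| Assumption | Missing | Difference of visit means | Paired change |
|---|---|---|---|
| No within-patient change on average | 20% | about +3.5 | 0.0 to 0.1 |
| same | 40% | about +6.5 | 0.0 to 0.1 |
| Scores regress to the mean (correlation 0.6), no change in the full group | 20% | +2.0 to +2.2 | −1.3 to −1.5 |
| same | 40% | +3.8 to +3.9 | −2.6 |

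Paired change removes the shift when change does not depend on the baseline score. Otherwise it remains an analysis of completers, so missing-form counts are needed beside it.

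**7. Does the protocol's 20% apply?** Protocol 10.1 gives 20% for patients lost, dead or progressed before day 56 without a first tumour assessment. That is not a rate of missing forms. SAP 3.1 assigns secondary efficacy endpoints to the PP population, and SAP 2 requires a baseline and a first tumour assessment for PP. If that rule governs quality of life, these patients are absent from the baseline row too, and their loss cannot create a baseline-to-week-8 shift. Section 4.8 names no population, and other secondary endpoints are also tabulated in ITT, so the documents leave this open.

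**The case against.** The strongest defence has four parts.

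- **The tables hold more than raw scores.** Each has a test against baseline. If it is a signed-rank test, it uses patients with both forms and addresses within-patient change. This stands in part: a reader might infer that nothing in the SAP compares with baseline, and that would be wrong. But the SAP does not say that the test is paired, and a p-value gives no size.
- **Cohort 1 patients are not left out.** A reader might infer from the heading of section 4.8 that they are never analysed. The documents do not support this: they are in the 16 pooled tables, and those in group B have tables of their own. What is missing is cohort 1 as the protocol defines it.
- **The format follows the protocol.** Section 10.7 prescribes N, mean, SD, median and range for continuous data, the endpoint is unsized, and cohort 2 is exploratory. This stands as a reason for modest severity. It does not turn visit summaries into the change that section 10.2 defines. The SAP already uses a suitable layout for corticosteroid dose: Table 135 gives a difference with N, mean, 95% CI, SD and median.
- **Drop-out bias is speculative, and each row prints its N.** This largely stands. A reader might infer that the means will drift upwards as sicker patients leave. That requires leavers to score lower, and the documents contain no quality-of-life data to show it.

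**Conclusion.** The point holds as a gap in estimation and reporting. Protocol 10.2 and 4.2 call for change from baseline in global health status in both cohorts; 0 of 40 tables give that change, its interval or a paired n, and none shows cohort 1 as such. The mismatch between w16 and week 24 compounds this, since one scheduled visit has no row. These findings rest on the text alone. The identification of cohort 1 with B + C follows from the group and cohort definitions.

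The drop-out effect is a possibility of unknown direction and size. The +1 to +4 points is an illustration that assumes 20% missing, leavers 5 to 20 points lower, no true change and a baseline row that includes the leavers. A reader might take the plan's 20% pre-day-56 loss as support for a week-8 shift of that size; the documents do not support this, because it is not a form-completion figure and those patients drop out of both rows under PP. The issue concerns a secondary endpoint, should be corrected, and does not touch the primary analysis.

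**What to change.** For global health status, in cohort 1, cohort 2 and pooled, report at each scheduled visit:

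- the number of patients with both the baseline and the visit form;
- the baseline mean in that same set;
- the mean and median paired change, with 95% CI;
- the numbers dead, progressed, or missing a form for other reasons.

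State that the Wilcoxon test is signed-rank, and name the analysis population for quality of life. Reconcile w16 in the shells with week 24 in the protocol, and say to which visit the tabulated forms belong. Keep the A + C and B tables as supplementary.

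The cost is re-programming of tables from data already collected, with Table 135 as a template. This assumes that forms were collected on the protocol's schedule; reconciling the visit labels will show whether they were.
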